4.10 Efficacy Evaluation

Not applicable(refer to Section [4.13](#)).

4.11 Safety Evaluation

All safety summaries and analyses will be based upon the Safety Set as defined in Section [4.6](#).

By-patient listings will include patient identifier, age, gender and race and will be sorted by patient, safety parameter and visit (if applicable).

4.11.1 Adverse Events

Adverse events (AEs) will be coded using the Medical Dictionary for Regulatory Activities (MedDRA) Version 23.0 and the Common Terminology Criteria for Adverse Events (CTCAE) Version 5.0.

An AE is any untoward medical occurrence in a study patient administered an IMP which does not necessarily have a causal relationship with this treatment. An AE can therefore be any unfavorable and unintended sign (including a clinically significant abnormal laboratory finding), symptom, or

disease temporally associated with the use of an IMP, whether or not considered related to the IMP. Adverse events may include the onset of new illness and the exacerbation of pre-existing conditions.

Other untoward events occurring in the framework of a clinical study will be recorded as AEs, e.g. those occurring during treatment-free periods (including post-treatment Follow-up period), in association with study-related procedures and assessments.

Concomitant illnesses, which existed before entry into the clinical study, will not be considered AEs unless they worsen during the treatment period. Pre-existing conditions will be recorded as part of the patient's medical history.

A treatment-emergent adverse event (TEAE) is defined as an AE that begins or that worsens in severity after at least one dose of the study drug has been administered.

Adverse event leading to study discontinuation is defined as an AE ongoing on the date of study discontinuation. Ongoing is defined as an AE started on or before and ended on or after the date of study discontinuation.

Summaries with number and percentage of patients reporting at least one adverse event and the total number of events will be reported by group and overall. Adverse event summaries will be provided separately for adverse events which occur or worsen from first dosing to Day 28 and adverse events which occur or worsen after Day 28.

- An overview on the number and percentage of patients with:
 - Any AE
 - Any AE of Grade 3 or higher
 - Any TEAE
 - Any TEAE of Grade 3 or higher
 - Any serious AE (SAE)
 - Any serious adverse drug reaction (SARs)
 - Any suspected unexpected serious adverse reaction (SUSARs)
 - Any treatment-emergent SAE
 - AE leading to death
 - TEAE leading to death
 - TEAE leading to treatment withdrawal
 - Any AE leading to study discontinuation

- TEAE leading to study discontinuation
- Number and percentage of patients for each TEAE, categorized by system organ class (SOC) and preferred term (PT)
- Number and percentage of patients for each TEAE of grade 3 or higher, categorized by SOC and PT
- Number and percentage of patients for each TEAE occurring in $\geq 5\%$ of subjects in any treatment group, categorized by SOC and PT
- Number and percentage of patients for each TEAE, categorized by SOC, PT, and maximum CTCAE grade
- Number and percentage of patients for each TEAE, categorized by SOC, PT, and relationship to study drug
- Number and percentage of patients for each TEAE of grade 3 or higher, categorized by SOC, PT, and relationship to study drug
- Number and percentage of patients for each treatment-emergent SAE, categorized by SOC, PT, and relationship to study drug

Adverse event summaries will be ordered in terms of decreasing frequency for SOC and PT within SOC in the Total group and then alphabetically for SOC and PT within SOC. Summaries will be ordered in terms of decreasing frequency for PT in the Total group in summaries where SOC is not included.

For each patient and each adverse event, the worst severity (highest CTCAE grade) recorded will be attributed and used in the by-severity summaries. Similarly, the worst causality (most related to treatment) will be attributed and used in the by-causality summaries. If CTCAE grade or causality is missing, a conservative approach for AE assessment (taking into account the worst case) will be followed.

A by-patient listing of all adverse events (including non-treatment-emergent events) will be provided. This listing will be presented by dose and will include patient identifier, age, sex, race, adverse event (SOC, PT, and verbatim term), date of onset, date of resolution, duration, severity, seriousness, outcome action taken (concerning both action with study drug and primary action (not related to study treatment)) and causality (concerning both study treatment and non-study treatment).

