Figure 3: The protective effect of ABX464 is maintained in mice during continuous DSS-treatment. (A) C57BL/6 mice (n=8 each cohort) were challenged with DSS for 63 days. Mice received orally once a day ABX464 in methylcellulose during the whole protocol (group 1) or only for the first 20 days followed by methylcellulose only administration (group 2). Mice of group 3 received methylcellulose during DSS-treatment and had to be scarified at day 10. (B) Weight development in ABX464-treated mice during DSS-administration. (C, D) Colons were analyzed by histology for lesion size (C) and colitis severity (D) at the end of the protocol. Histological scoring was performed as stated above.

In humans, ABX464 is rapidly metabolized into one main metabolite, ABX464-N-Glucuronide. (ABX464-N-Glu). Thus, ABIVAX studied in the same DSS-mice model the efficacy of the ABX464-N-Glucuronide. Like ABX464, in the same DSS-mice model, ABX464-NGlu (40 mg/kg) protects mice from DSS-induced weight loss (Figure 53). This finding has substantial implications in light of treating inflammatory ulcerative colitis (UC) disease since studies in healthy patients demonstrated that:

- ABX464-NGlu C_{max} was approximately 160-fold higher than those of ABX464 and had a much longer t_{1/2} (90 to 110 hours) than the parent compound (2-3 hours), resulting in a > 1000-fold difference in AUC between the 2 compounds.
- The markedly higher plasma concentrations of ABX464-N-Glu, and its ability to protect mice from DSS-induced colitis, may allow the use of lower doses of the parent compound ABX464 for a longer period in UC patients.

[figure not shown]

Figure 4: ABX464-N-Glu treatment suppresses disease severity in DSS-induced colitis. (A) C57BL/6 mice (n=10 for DSS and n=9 for DSS + ABX464 and for DSS + ABX464 N-Glucuronide) subjected to the DSS colitis protocol shown received orally once a day ABX464 40 mg/kg (DSS + ABX464, in green), or ABX464-N-Glucuronide 40 mg/kg (DSS + ABX464 N-Glucuronide, in orange) in methylcellulose or methylcellulose only (DSS, in red) through gavage. (B) Weight development in ABX464, in ABX464-N-Glu and methylcellulose only treated mice during DSS-induced colitis

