8. ADVERSE EVENTS (AE) AND SERIOUS ADVERSE EVENTS (SAE)

The investigator is responsible for the detection and documentation of events meeting the criteria and definition of an AE or SAE. During the study, in case of a safety evaluation, the investigator or site staff will be responsible for reporting AEs and SAEs, as detailed in this section of the protocol.

All adverse events (Serious and non-serious) will be collected from the time of signing of ICF and until D48 visit.

Any disease progression will be both reported in the eCRF as an adverse event and documented in the efficacy section.

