8.3.2. Clinical laboratory parameters

Abnormal laboratory findings (e.g., clinical chemistry, hematology) or other abnormal assessments (e.g. vital signs) that are judged by the investigator as **clinically significant** will be recorded as AEs or SAEs if they meet the definitions of section 8.1. Clinically significant abnormal laboratory findings or other abnormal assessments that are detected during the study or are present at informed consent and significantly worsen during the study will be reported as AEs or SAEs. Clinically significant abnormal laboratory findings or other abnormal assessments that are associated with the disease being studied and are present at the start of the study will be recorded as medical history and will be reported as AEs or SAEs in case of worsening.

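### SAP 4.11.1 limits adverse events in pre-existing illness to worsening in the treatment period, which conflicts with the protocol's collection window to D48 and with other sentences in the same SAP section

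*SAP*

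**What the plan says.** SAP 4.11.1 gives a specific rule for illness present before entry: "Concomitant illnesses, which existed before entry into the clinical study, will not be considered AEs unless they worsen during the treatment period". SAP Table 1 (section 4.2.3) runs the Treatment Period from Visit 1 to Visit 5. The Safety Follow-up Period starts the day after Visit 5 and ends at Visit 6, which is targeted at Day 48.

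The same SAP section also says:
- "Adverse events may include the onset of new illness and the exacerbation of pre-existing conditions", with no time limit.
- Other untoward events are recorded as AEs, with the example of "those occurring during treatment-free periods (including post-treatment Follow-up period".
- A TEAE is an AE that starts or becomes more severe after at least one dose. No end date is given.
- Summaries are split at Day 28, and the later part covers "adverse events which occur or worsen after Day 28".

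SAP 2.2 keeps one secondary objective, safety from D0 to D48.

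The protocol is broader than the restrictive SAP sentence. Section 8 says: "All adverse events (Serious and non-serious) will be collected from the time of signing of ICF and until D48 visit". Section 8.1.1 counts exacerbated as well as new disease, and designates events in the pre- and post-treatment periods as AEs. Section 8.5 requires recording until 21 days after the product is completed or stopped. For abnormal laboratory findings and other abnormal assessments, section 8.3.2 says that those which "are present at informed consent and significantly worsen during the study will be reported as AEs or SAEs". Section 9.2 defines two TEAE periods. The first, to Day 28, refers to events that occur or worsen; the second, after Day 28, refers only to events that occur.

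**The concern.** Patients qualify by having at least one listed risk factor: age 65 or over, obesity, recent uncontrolled hypertension, treated diabetes or a history of ischaemic cardiovascular disease. Apart from age, these are pre-existing conditions, so worsening of an existing illness is a foreseeable form of harm in this trial. After the futility decision, SAP version 5.0 has no efficacy analyses, and the AE tables are among its main outputs.

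If the restrictive sentence is programmed or applied as written, late worsening of such conditions would be recorded by sites but left out of the AE and TEAE counts for the follow-up period. If the other sentences are followed, it would be counted. Two programmers working from the same section could produce different after-Day-28 tables.

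**Working it through.** The point concerns a definition, and the plan gives no figure to reproduce. The check runs three hypothetical records through each rule, with Visit 5 on D28 and Visit 6 on D48.

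**Record A: treated diabetes present at entry, first worsens on D35.**
1. Period: D35 is after Visit 5 and before Visit 6, so Table 1 places it in Safety Follow-up.
2. Protocol: D35 is before D48 (section 8), exacerbated disease is an AE (8.1.1), and the event is within 21 days of the end of treatment (8.5). It is recorded as an AE.
3. SAP restrictive sentence, read with Table 1: the worsening is outside the Treatment Period, so it is not an AE.
4. SAP general definition and follow-up sentence: it can be an AE.
5. SAP TEAE definition and after-Day-28 summaries: both select from adverse events. They include the record if step 4 governs and exclude it if step 3 governs. They do not settle the matter themselves.

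**Record B: an AE that begins on D20 and worsens on D35.** It is already an AE, so it enters the after-Day-28 summary under either reading.

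**Record C: a new illness with onset on D35.** The restrictive sentence does not apply, so it is counted under either reading.

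The conflict is therefore confined to records of type A.

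**Context only.** The contested interval is 48 − 28 = 20 days, and 20/48 = 42% of the nominal D0 to D48 calendar. Protocol 1.4.2 gives the main metabolite a half-life of 90 to 110 hours. Assuming first-order decline, the fraction left d days after the last dose is 0.5^(24d/h):

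| Days after last dose | h = 90 | h = 110 |
|---|---|---|
| 7 | 0.5^1.87 = 27.4% | 0.5^1.53 = 34.7% |
| 14 | 0.5^3.73 = 7.5% | 0.5^3.05 = 12.0% |
| 21 | 0.5^5.60 = 2.1% | 0.5^4.58 = 4.2% |

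Exposure thus continues through much of follow-up, with little left at its end. Neither the 42% nor the washout figures count misclassified events. They show only that the interval is not trivial.

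**The case against.** A reader might infer that these events are dropped, or that the after-Day-28 tables hold only new-onset events. The documents do not support either inference. The protocol governs what sites record and requires these events. No derivation in SAP 4.11.1 or 4.11.2 matches AE records to medical history or filters them by period. The SAP also plans a listing of all adverse events, including those that are not treatment-emergent. Record B shows that worsening of an AE already under way stays in the later tables even on the strict reading.

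It can also be said that the strict reading is a choice. The sentence uses the term treatment period in lower case and does not cite Table 1. The sentence after it sends pre-existing conditions to medical history, which suggests that the aim is to keep stable baseline illness out of the AE data. Protocol 8.3.2 concerns abnormal assessments, not illness in general, so the authority for illness is 8.1.1 with sections 8 and 8.5.

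All of this limits the claim, but it does not remove the conflict. The TEAE definition and the after-Day-28 summaries apply only to what is already an AE, and the restrictive sentence is the one rule written specifically for pre-existing illness. The permissive sentences are general. A stated rule that gives the wrong table when followed literally should be corrected, even if a sympathetic reader would apply it otherwise.

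**Conclusion.** SAP 4.11.1 contains a definition that conflicts with the protocol's AE definition and collection window, with the SAP's own D0 to D48 safety objective, and with other sentences of the same section. Read literally, it excludes from the AE and TEAE tables a pre-existing illness that first worsens between Visit 5 and the D48 visit, and so could understate after-Day-28 events. How many events are affected, and whether there are any, cannot be derived from the documents.

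The conclusion rests on two assumptions: that treatment period in SAP 4.11.1 has the meaning Table 1 gives it, and that sites recorded events as the protocol requires. If the first fails, the sentence is ambiguous rather than restrictive, and the same correction is needed. The point merits a change before the tables are relied on. It does not support a statement that safety data were lost or that harm was understated.

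**What to change.** In SAP 4.11.1:
- Replace the limit to the treatment period with: *from informed consent to the end of protocol AE collection (D48 visit, or 21 days after last study drug intake)*. Starting the window at the first dose instead would leave out worsening between consent and first dose. The protocol collects from consent and lets Visit 1 be split by up to 48 hours, and the SAP overview reports any AE separately from any TEAE.
- Keep the TEAE definition unchanged as the criterion for events on or after the first dose.
- State that worsening of a pre-existing illness after Day 28 enters the after-Day-28 summaries.

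Align protocol 9.2, whose later period mentions only occurrence, with the SAP, which includes worsening. If the protocol is no longer being amended, SAP 4.13 can record the difference. The end of the window should be confirmed at the same time, because the note in protocol 8.1.1 extends reporting to four weeks after the end of treatment, while sections 8 and 8.5 give D48 and 21 days. These passages need to be reconciled.

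The cost is a few lines of text and a check that no program excludes such records. No new data are needed, since protocol 8.5 already requires the events in the eCRF.

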7.2. Patient Premature trial discontinuation

A patient can be withdrawn at any time from the study. Premature trial discontinuation could occur for the following reasons:

- Investigator's decision.
- An Adverse Event or an intercurrent condition that preclude continuation of treatment. Specifically, an elevation $\geq 3.0 \times$ ULN in liver transaminases (AST/SGOT and/or ALT/SGPT) or Alkaline phosphatase or in total bilirubin compared to baseline requires close observation with repeating liver enzymes and serum bilirubin tests every 2 days. Discontinuation of the study treatment should occur if:
 - ALT or AST $> 8 \times$ ULN
 - ALT or AST $> 3 \times$ ULN and total bilirubin $> 2 \times$ ULN or INR > 1.5
 - ALT or AST $> 3 \times$ ULN with appearance of fatigue, nausea, vomiting, right upper quadrant pain or tenderness, fever, rash, and/or eosinophilia ($> 5\%$).
 - Alkaline Phosphatase $\geq 2.0 \times$ ULN
- Serious adverse event with suspected causal relationship to the IMP
- Any relevant toxicity or negative change in the risk/benefit assessment leading to an unacceptable risk for the patient (i.e. occurrence of adverse events which character, severity or frequency is new in comparison to the existing risk profile), or any data deriving from other clinical trials or toxicological studies which negatively influence the risk/benefit assessment.
- Major protocol violation.
- Withdrawal of consent.
- Administrative reasons from Sponsor.

A patient who prematurely exits the study will not be replaced.

All patients, regardless of the completion or premature discontinuation, should come back for an on-site safety follow-up visit 21 days after the last study drug intake, and all examinations must be performed according to the study flow-chart.

The same long-term follow-up will be performed as described in section 7.1 providing the reason for premature discontinuation is not "withdrawal of consent".

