8.3.3. Pregnancy report

Patients who become pregnant at any time will be immediately withdrawn from participation in the study. All appropriate withdrawal assessments may be performed at the discretion of the investigator.

The investigator will collect pregnancy information on any woman patient or partner of a male patient, who becomes pregnant and their partner while participating in this study. The investigator will record pregnancy information on a specific pregnancy notification form and submit it to ABIVAX or its designee within 24 hours after knowledge of a patient's or partner's pregnancy. The patient or partner will also be followed to determine the outcome of the pregnancy, be it full-term or prematurely terminated. Information on the status of the mother and child will be forwarded to ABIVAX or its designee. Follow-up will end 6 to 8 weeks following the estimated delivery date.

While pregnancy itself is not considered to be an AE or SAE, any pregnancy complication or elective termination of a pregnancy for medical reasons will be recorded as an SAE. A spontaneous abortion is always considered to be an SAE and will be reported as such.

The time period for collecting pregnancy information is identical to the time period for collecting AEs, as stated in Section 8.4, Time Period, Frequency, and Method of Detecting AEs and SAEs.

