4.5 Study Patients

4.5.1 Disposition of Patients

A clear accounting of the disposition of all patients who enter the study will be provided, from screening to study completion.

Disposition summaries will be provided by treatment and overall. Number and percentage of patients with ICF, randomized and treated with any amount of study drug will be provided by country and overall). Number and percentage of patients who entered, completed and discontinued (with reason for discontinuation) a study period will be provided separately for treatment and follow up period.

Summary will include:

- the number of subjects randomized
- the number and percentage of subjects treated with any amount of study drug
- the number and percentage of subjects entering, withdrawing from study treatment, withdrawing from the study and completing each phase of the study by treatment group and overall. Withdrawals from the study and from study treatment will also be summarized by major reason.

By-patient listings of eligibility and randomization details, visit dates, and withdrawal details (including reason for discontinuation and duration of treatment prior to discontinuation) will also be provided.

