4.11.2 Deaths, Serious Adverse Events, and Other Significant Adverse Events

Other significant adverse events are those adverse events reported as leading to an intervention e.g. withdrawal from study, discontinuation of study treatment, introduction of concomitant medication, dose reduction. Following the specification provided for adverse AE summaries at section 4.11.1 summaries detailed below will be provided for deaths, SAEs and other significant AEs:

- Number and percentage of patients for each TEAE leading to death, categorized by SOC and PT
- Number and percentage of patients for each treatment-emergent SAE, categorized by SOC and PT
- Number and percentage of patients for each TEAE leading to study discontinuation, categorized by SOC and PT
- Number and percentage of patients for each TEAE leading to treatment withdrawal, categorized by SOC and PT

For deaths, SAEs and other significant AEs the following listings will be provided:

- A by-patient listing of all deaths that occurred during the study
- A by-patient listing of all serious treatment-emergent adverse events
- A by-patient listing of all TEAE leading to treatment withdrawal
- A by-patient listing of all TEAE leading to study discontinuation

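### The SAP flags an AE as leading to study discontinuation by date overlap alone, ignoring the recorded reason for leaving

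*SAP*

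**What the plan says.** The rule is in SAP 4.11.1 and has two sentences: "Adverse event leading to study discontinuation is defined as an AE ongoing on the date of study discontinuation" and "Ongoing is defined as an AE started on or before and ended on or after the date of study discontinuation". The revision history shows it was added as derivation logic in SAP version 5.0.

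The flag supplies two rows of the AE overview in 4.11.1 (any AE, and TEAE, leading to study discontinuation). In SAP 4.11.2 it supplies a table, "Number and percentage of patients for each TEAE leading to study discontinuation, categorized by SOC and PT", and a by-patient listing.

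Four other places bear on it:

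- SAP 4.11.2 describes the wider class of events differently: "Other significant adverse events are those adverse events reported as leading to an intervention e.g. withdrawal from study".
- SAP 4.5.1 shows that a reason for leaving is available: "Withdrawals from the study and from study treatment will also be summarized by major reason". The reason is also listed by patient.
- Protocol 7.2 gives seven reasons for premature trial discontinuation, among them "Administrative reasons from Sponsor".
- Protocol 8.3.3 adds a further route out of the study: "Patients who become pregnant at any time will be immediately withdrawn from participation in the study".

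**The concern.** A reader takes *leading to* as a statement of cause. The rule tests only whether an AE was present on a given day. The two differ whenever a patient leaves for a reason other than an AE while some AE happens to be open, and whenever the AE that drove the exit had closed before the exit date was recorded.

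Overlap by chance is plausible in this trial. Protocol section 8 requires disease progression to be reported as an AE as well as in the efficacy section, so COVID-19 worsening itself can be the overlapping event.

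After the futility decision all efficacy analyses were removed (SAP 4.13), so the safety tables are the substance of the report. The same patient could appear under withdrawal of consent in the disposition table and as an AE discontinuation in the safety table.

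**Working it through.** The plan states no figure for this flag, so there is nothing to reproduce. The check applies the written rule to the situations the documents allow.

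**The rule as written.** With S the AE start date, E its end date and D the study discontinuation date, flag = (S ≤ D) and (E ≥ D). There is no term for the reason and no branch for a missing E.

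**1. Reasons the rule cannot tell apart.** Of the seven reasons in Protocol 7.2, three are not AEs: major protocol violation, withdrawal of consent, and sponsor administrative reasons. A fourth, the investigator's decision, need not be one. The rule treats all seven alike. Pregnancy gives a case that is wrong on the protocol's own terms. The patient must leave, and Protocol 8.3.3 also says "While pregnancy itself is not considered to be an AE or SAE". Any unrelated AE that spans that day is still flagged as the cause.

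**2. End dates.**

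- Protocol 7.2 asks patients who stop early to return 21 days after their last dose, so a causal AE can close before the patient leaves the study.
- Protocol 8.6 allows on-going as an AE outcome, and SAP 4.3.1 leaves a stop date missing when its year is unknown. Neither kind of record has an E that can satisfy E ≥ D.
- SAP 4.3.1 moves a partial stop date to the end of the month, or to December if the month is unknown. This can create overlap where there was none.

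**3. Six hypothetical AE records, with D = 10 March 2021.**

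| Record | S | E | AE caused exit? | Literal rule | Rule if missing E counts as ongoing |
|---|---|---|---|---|---|
| Consent withdrawn, unrelated AE open | 1 Mar | 15 Mar | No | Flagged (wrong) | Flagged (wrong) |
| Exit for sponsor termination, AE open | 20 Feb | 20 Mar | No | Flagged (wrong) | Flagged (wrong) |
| Causal AE, resolved before D | 20 Feb | 5 Mar | Yes | Not flagged (wrong) | Not flagged (wrong) |
| Causal AE, no end date | 1 Mar | missing | Yes | Not flagged (wrong) | Flagged (right) |
| Causal AE, ends after D | 1 Mar | 20 Mar | Yes | Flagged (right) | Flagged (right) |
| Non-causal AE, end known only as March, set to 31 Mar | 1 Mar | 31 Mar | No | Flagged (wrong) | Flagged (wrong) |

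Treating a missing end date as ongoing repairs one record. The other four errors need the recorded reason.

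**4. Effect of one misclassified patient on an arm percentage.**

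- At the planned 800 (533:267): 1/533 = 0.188% and 1/267 = 0.375%.
- At 300 split 2:1 (200:100): 1/200 = 0.5% and 1/100 = 1.0%.

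The 300 is the planned interim size, used here only as a smaller reference point. The actual denominator is the Safety Set, whose size the documents do not give.

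**5. Illustration on assumed shares.** None of these shares comes from the documents. Let q be the share of discontinued patients who left because of an AE (10% to 30%), r the share of the others with an overlapping AE (20% to 50%), and s the share of causal AEs closed before D (10% to 40%). The fraction of flagged patients who truly left because of an AE is q(1−s) / [q(1−s) + (1−q)r].

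- Lowest: q = 0.1, r = 0.5, s = 0.4 gives 0.06/(0.06 + 0.45) = 0.12.
- Highest: q = 0.3, r = 0.2, s = 0.1 gives 0.27/(0.27 + 0.14) = 0.66.

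This shows only that the flag can be a poor marker of cause. The conclusion does not depend on it.

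**The case against.** The strongest reply is that this is a descriptive flag whose definition is stated openly. Listings give the withdrawal reason and the onset and resolution dates of each AE, so a careful reader can reconcile individual cases. The treatment-withdrawal outputs, which carry the main tolerability information, are separate. No difference in misclassification between arms has been shown. All of this is true and limits the seriousness. It does not make the label correct: a summary table should not need patient-by-patient correction from listings.

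Further points, and what stands of each:

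- *SAP 4.11.2 does not set a rival rule.* Its summaries are said to follow 4.11.1, and its wording is a general description. That is fair. What remains is that the section describes reported cause while its tables are built on dates.
- *A missing end date would naturally be read as ongoing.* The rule's first sentence supports that reading, and the SAP leans conservative elsewhere: AEs with unknown start dates count as treatment-emergent, and missing grade or causality takes the worst case. This is the weakest of the three failures and holds only on a literal reading, but the SAP should say which reading applies.
- *Pregnancy will be rare,* given the contraception requirement. Agreed. It shows the logic and not the frequency; withdrawal of consent makes the same point.
- *Sponsor termination may not have given patients a discontinuation date.* The documents do not say, so no weight is placed on it.
- *The outputs are more than two rows and one table.* SAP 4.11.1 splits AE summaries at Day 28, so the count given here is of distinct outputs and not of pages.

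**Conclusion.** The rule is wrong as written. A label that claims cause is assigned by coincidence in time, so following the SAP exactly counts unrelated AEs and omits causal AEs that had resolved. Read literally, it also omits causal AEs with no end date.

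The damage is confined to descriptive safety outputs: two overview rows, one SOC/PT table and one listing. The number misclassified, and the net direction, cannot be determined from the documents. Each case is worth 0.19 points on ABX464 and 0.37 points on placebo at planned size, and more in a smaller Safety Set. This should be fixed before the safety report is produced, but it does not touch any test or stopping decision.

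The first two failures follow directly from the wording. The third assumes that no unwritten convention treats a missing end date as ongoing.

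**What to change.** Replace the two sentences in SAP 4.11.1 so that an AE is flagged only when both conditions hold:

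1. The recorded reason for study discontinuation is an adverse event or death.
2. The AE is the one the investigator identified as that reason, or the fatal AE.

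The first condition uses the disposition reason that SAP 4.5.1 already summarizes. The second needs a link from the AE to the exit, and the documents do not show whether the eCRF holds one. The AE listing in 4.11.1 includes an action field not related to study treatment; its content is not described, so check whether it supplies the link. The permanent-discontinuation entry in Protocol 8.6 should not stand in for it, because it concerns the investigational product and not leaving the study.

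If there is no link, keep the date rule but rename the two overview rows, the SOC/PT table and the listing as AEs ongoing at study discontinuation. State that AEs without an end date count as ongoing, and cross-tabulate by disposition reason.

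The cost is one or two SAP sentences and one extra programming condition. The relabelling option needs no new data.
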